### 8.2.2 Patient Eligibility

The following four new user cohorts based on available data in a claims database will be created: (1) erenumab-aooe, (2) other mAbs targeting the CGRP pathway, (3) selected SOC migraine preventive medications (anti-epileptics), and (4) onabotulinumtoxinA. The index date is defined as the date of first claim for each of these group of medications. Use of mAbs targeting the CGRP pathway based on free/discount/coupon programs is not captured in claims data, therefore in the current protocol the term "new users" for these medications refers to the first appearance of a claim for the medication in the claims database and not necessarily the first time the patient has used the medication. Because treatment guidelines recommend inadequate response or intolerance to two SOC migraine preventive medications prior to erenumab initiation, the SOC anti-epileptic preventive medication cohort and the botulinum toxin cohort will be selected from the remaining population of migraine patients after the erenumab and other CGRP mAbs cohorts have been created.

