### 8.2.2.1 Inclusion Criteria

Patients must meet the following inclusion criteria:

- 1. 18-64 years of age on the index date.
- 2. One year of continuous enrollment (ie, complete medical and pharmacy coverage) prior to and including the index date, which defines the baseline period.
- 3. A diagnosis of migraine during the baseline period, based on one of the following criteria:
  - a) ≥1 inpatient claim with a diagnosis of migraine (ICD-10-CM) diagnosis code of G43.xxx).
  - b) ≥1 outpatient evaluation and management claim with a diagnosis of migraine and a specialty code of 260 (neurologist).
  - c)  $\geq 1$  claim for emergency room visit with a diagnosis of migraine.
  - d) ≥1 outpatient evaluation and management claim with a diagnosis of migraine PLUS ≥1 pharmacy fill for a migraine-specific triptan or an ergotamine class medication within 365 days of each other
  - e) ≥2 outpatient evaluation and management claims with a diagnosis of migraine between 7 and 365 days apart.
  - f) ≥2 pharmacy fills for migraine-specific triptans or ergotamine class medications between 7 and 365 days apart.

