### 8.2.5 Study Follow-up

Follow-up will be evaluated in two ways. With an 'intention-to-treat' analysis, patients will be followed for all available time after they initiate a medication, irrespective of whether they discontinue the medication or not, or whether they switch to an alternate medication or not. Follow-up begins the day after the index date and ends at first occurrence of: (a) the outcome of interest, (b) disenrollment from a health plan, or (c) end of study period.

With a 'per-protocol analysis' patients are followed for as long as they are actively taking the medication of interest during the follow-up period. Follow-up begins the day after the index date and ends at first occurrence of: (a) the outcome of interest, (b) disenrollment from the health plan, (c) discontinuation of study medication, (d) switching to the alternate medication, or (e) administrative end of study. When a gap greater than the allowable gap of 30 days is encountered, discontinuation of study medication occurs at the end of the last prescription which includes the days supply (+60 day extension). Censoring due to switching will occur for the new user cohorts in this study when the following conditions are met:

- (1) For new users of erenumab-aooe, initiation of any other medication targeting the CGRP pathway (galcanezumab-gnlm, fremanezumab-vfrm, eptinezumab-jjmr, ubrogepant, rimegepant) during the follow-up period.
- (2) For new users of other mAbs targeting the CGRP pathway, initiation of erenumab-aooe, ubrogepant, or rimegepant during the follow-up period.
- (3) For new users of the SOC migraine preventive medications (anti-epileptics), initiation of any medication targeting the CGRP pathway (erenumab-aooe, galcanezumab-gnlm, fremanezumab-vfrm, eptinezumab-jjmr, ubrogepant, rimegepant) during the follow-up period.
- (4) For new users of onabotulinumtoxinA, initiation of any medication targeting the CGRP pathway (erenumab-aooe, galcanezumab-gnlm, fremanezumab-vfrm, eptinezumab-jjmr, ubrogepant, rimegepant) during the follow-up period.

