### 8.3.2 Outcome Assessment

The outcomes of interest are hypertension, acute MI, and stroke, which will be identified within the MarketScan® claims database using ICD-10-CM diagnosis codes. The following algorithms will be used for each of the outcomes:

- Hypertension occurrence of one inpatient (IP) diagnosis, one emergency room (ER) diagnosis, or one outpatient (OP) diagnosis during the follow-up period.
- (2) Acute MI occurrence of one diagnosis in the IP setting during the follow-up period.
- (3) Stroke, including both ischemic stroke and hemorrhagic stroke occurrence of one diagnosis in the IP setting during the follow-up period.

All outcomes will be assessed separately starting from the index date through the end of follow-up as described in Section 8.2.5. Only the first (incident) event for each outcome will be included in the analysis. The ICD-10-CM diagnosis codes for hypertension acute MI, and stroke are provided in Appendix C. The validation studies supporting the algorithms and ICD-10-CM diagnosis codes for the outcomes evaluated in this study are

provided in Section 8.3.4. The negative control outcomes that will be used to evaluate exchangeability between study cohorts for the comparative analyses are described in Section 8.7.2.4.

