163.549	ICD-10-CM Diagnosis	Cerebral infarction due to unspecified occlusion or stenosis of unspecified cerebellar artery	1 IP
163.59	ICD-10-CM Diagnosis	Cerebral infarction due to unspecified occlusion or stenosis of other cerebral artery	1 IP
163.6	ICD-10-CM Diagnosis	Cerebral infarction due to cerebral venous thrombosis, nonpyogenic	1 IP
163.8	ICD-10-CM Diagnosis	Other cerebral infarction	1 IP
163.81	ICD-10-CM Diagnosis	Other cerebral infarction due to occlusion or stenosis of small artery	1 IP
163.89	ICD-10-CM Diagnosis	Other cerebral infarction	1 IP
163.9	ICD-10-CM Diagnosis	Cerebral infarction, unspecified	1 IP

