### Hemorrhagic Stroke Codes

Code	Code type	Code description	Setting (Any diagnosis position)
160	ICD-10-CM Diagnosis	Nontraumatic subarachnoid hemorrhage	1 IP
160.0	ICD-10-CM Diagnosis	Nontraumatic subarachnoid hemorrhage from carotid siphon and bifurcation	1 IP
160.00	ICD-10-CM Diagnosis	Nontraumatic subarachnoid hemorrhage from unspecified carotid siphon and bifurcation	1 IP
l60.01	ICD-10-CM Diagnosis	Nontraumatic subarachnoid hemorrhage from right carotid siphon and bifurcation	1 IP
160.02	ICD-10-CM Diagnosis	Nontraumatic subarachnoid hemorrhage from left carotid siphon and bifurcation	1 IP
160.1	ICD-10-CM Diagnosis	Nontraumatic subarachnoid hemorrhage from middle cerebral artery	1 IP

Code	Code type	Code description S	
160.10	ICD-10-CM Diagnosis	Nontraumatic subarachnoid hemorrhage from unspecified middle cerebral artery	1 IP
160.11	ICD-10-CM Diagnosis	Nontraumatic subarachnoid hemorrhage from right middle cerebral artery	1 IP
160.12	ICD-10-CM Diagnosis	Nontraumatic subarachnoid hemorrhage from left middle cerebral artery	1 IP
160.2	ICD-10-CM Diagnosis	Nontraumatic subarachnoid hemorrhage from anterior communicating artery	1 IP
160.20	ICD-10-CM Diagnosis	Nontraumatic subarachnoid hemorrhage from unspecified anterior communicating artery	1 IP
160.21	ICD-10-CM Diagnosis	Nontraumatic subarachnoid hemorrhage from right anterior communicating artery	1 IP
160.22	ICD-10-CM Diagnosis	Nontraumatic subarachnoid hemorrhage from left anterior communicating artery	1 IP
160.3	ICD-10-CM Diagnosis	Nontraumatic subarachnoid hemorrhage from posterior communicating artery	1 IP
160.30	ICD-10-CM Diagnosis	Nontraumatic subarachnoid hemorrhage from unspecified posterior communicating artery	1 IP
160.31	ICD-10-CM Diagnosis	Nontraumatic subarachnoid hemorrhage from right posterior communicating artery	1 IP
160.32	ICD-10-CM Diagnosis	Nontraumatic subarachnoid hemorrhage from left posterior communicating artery	1 IP
160.4	ICD-10-CM Diagnosis	Nontraumatic subarachnoid hemorrhage from basilar artery	1 IP
160.5	ICD-10-CM Diagnosis	Nontraumatic subarachnoid hemorrhage from vertebral artery	1 IP
160.50	ICD-10-CM Diagnosis	Nontraumatic subarachnoid hemorrhage from unspecified vertebral artery	1 IP
160.51	ICD-10-CM Diagnosis	Nontraumatic subarachnoid hemorrhage from right vertebral artery	1 IP
160.52	ICD-10-CM Diagnosis	Nontraumatic subarachnoid hemorrhage from left vertebral artery	1 IP

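### Stroke follow-up starts the day after index and no lagged analysis is planned, so strokes already under way at index may be counted as drug events and may bias the erenumab versus anti-epileptic risk ratio downward.

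*Protocol*

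**What the plan says.** **Start of follow-up.** Protocol 8.2.5 uses the same start for the intention-to-treat and per-protocol analyses: "Follow-up begins the day after the index date and ends at first occurrence of: (a) the outcome of interest". Section 8.3.2 differs by one day: "All outcomes will be assessed separately starting from the index date through the end of follow-up as described in Section 8.2.5". Neither section sets a lag or induction period. Section 8.3.2 adds: "Only the first (incident) event for each outcome will be included in the analysis".

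**Stroke outcome.** Section 8.3.4 pools ischemic and hemorrhagic events for the primary analysis and also describes them separately. In Appendix C the ischemic list (inpatient, primary position) contains "Cerebral infarction due to cerebral venous thrombosis, nonpyogenic". The hemorrhagic list (inpatient, any position) opens with "Nontraumatic subarachnoid hemorrhage" and goes on to intracerebral hemorrhage. Prior stroke is a baseline covariate and a stratum, not an exclusion.

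**Entry.** Under 8.2.2.1, criterion 3c, a single "claim for emergency room visit with a diagnosis of migraine" is enough, and the migraine code table in Appendix C agrees. Section 8.9.1.2 says instead that the anti-epileptic and onabotulinumtoxinA cohorts must show two pieces of migraine evidence (diagnosis codes, treatment prescriptions or both).

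**Place in therapy.** Section 8.2.2 states that "treatment guidelines recommend inadequate response or intolerance to two SOC migraine preventive medications prior to erenumab initiation". Section 8.9.4 says the antibody cohorts will contain prevalent as well as incident users.

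**Estimates and sensitivity analyses.** Section 8.7.2.4 reports cumulative risk ratios at 6 months, 1 year and 2 years and plots the whole curve. Section 8.7.2.5 contains stratified analyses and a high-dimensional propensity score. Section 8.9.1.4 adds a bias analysis for smoking. None of these changes when stroke counting starts.

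**The concern.** Some conditions on the stroke list can first show themselves as headache. This is general clinical knowledge that the protocol does not state, and I treat it as an assumption. Such a headache can be coded as migraine in an emergency room and a preventive prescribed, with the stroke recognized at an admission days later. The plan then counts the stroke against the drug just started.

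If this happened equally in all arms, it would only dilute the ratio. It may not be equal. A drug recommended after two others have failed, in cohorts that include prevalent users, is on average started further from the first headache presentation than an anti-epileptic. Extra early strokes among anti-epileptic starters raise the denominator of the ratio in the second contrast and lower the ratio. In a safety study that is the direction that conceals harm.

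Baseline covariates cannot adjust for a stroke not yet diagnosed at index. The negative controls listed in 8.7.2.4 (accidents, fractures, vaccinations, screening and the like) are not conditions that present as headache, so the comparability assessment would not reveal the problem. Because risks are cumulative from the start of follow-up, the early events stay in the estimate at every horizon.

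**Working it through.** **The plan's own figures.** Table 3 gives a detectable stroke ratio of 1.46 for 20,000 per arm, 80% power, alpha 0.05 and 0.60 strokes per 100 person-years. With two-sided alpha and one year per patient (both assumed), this does not reproduce: Schoenfeld, arcsine and Freedman calculations give 1.39 to 1.40, and 1.46 has about 90% power. The size of 3,750 per arm for a ratio of 2.0 in 8.7.2.4 does reproduce approximately: 66 events / (0.006 + 0.012) = 3,667. The Table 3 mismatch is a separate matter and nothing below depends on it.

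**Attenuation.** Let e be the added risk of already-developing strokes, in the anti-epileptic arm only. It is not in the documents; I assume 2, 5 and 10 per 10,000.

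Observed RR(t) = [1 - exp(-0.006 × RR × t)] / [1 - exp(-0.006 × t) + e]

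Comparator risks without e are 0.2996% (6 months), 0.598% (1 year) and 1.193% (2 years). With a true ratio of 1.5 the erenumab risks are 0.449%, 0.896% and 1.784%.

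| Horizon | e = 2 per 10,000 | e = 5 per 10,000 | e = 10 per 10,000 |
|---|---|---|---|
| 6 months | 0.449/0.3196 = 1.41 | 0.449/0.3496 = 1.28 | 0.449/0.3996 = 1.12 |
| 1 year | 0.896/0.618 = 1.45 | 0.896/0.648 = 1.38 | 0.896/0.698 = 1.28 |
| 2 years | 1.784/1.213 = 1.47 | 1.784/1.243 = 1.44 | 1.784/1.293 = 1.38 |

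A true ratio of 1.0 reads 0.94, 0.86 or 0.75 at 6 months.

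**Scale.** In 20,000 starters these assumptions mean 4, 10 or 20 strokes. The plan's rate gives 20,000 × 0.006 × 30/365 = 9.9 strokes in 30 days. The hemorrhagic rate of 1.00 per 1,000 person-years in 6.3 gives 20,000 × 0.001 × 30/365 = 1.6.

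**Power at 1 year** (20,000 per arm, true ratio 1.46, pooled two-proportion test; 0.006 × 1.46 = 0.00876):

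- 5 extra anti-epileptic strokes: observed ratio 1.40, power 83%.
- 10 extra: 1.35, 74%.
- 20 extra: 1.25, 51%.
- To bring 1.46 down to 1.00: (0.00876 - 0.006) × 20,000 = 55 extra, or 46% of the 120 strokes expected in a year.
- If one third as many also arise under erenumab, 20 extra give 1.30 (65%). If both arms are equally affected, 20 give 1.39 (86%).
- True ratio 2.0, 40 extra: 0.012 / 0.008 = 1.50, power at least 98%.

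**Cost of a lag.** A 30-day lag leaves 120 × 335/365 = 110 expected comparator strokes in the first year. Power for 1.46 falls from 89.7% to 87.0%.

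**The case against.** The strongest objection is that neither the number of such strokes nor their split between arms is documented. Section 8.2.2 reports a guideline recommendation; eligibility does not require two failed preventives. The anti-epileptic cohort is barred only from anti-epileptics and CGRP drugs in the prior year, so its members may have tried other preventives. Section 8.7.2.4 also says that antibody starters may be sicker, which is a separate influence in the opposite direction. All of this stands, and it is why the asymmetry can be called plausible and no more.

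Second, the pathway relies partly on entry through one emergency room claim, which 8.9.1.2 contradicts for the anti-epileptic and onabotulinumtoxinA cohorts. This also stands: the two sections cannot both apply. If two pieces of evidence are required, the route narrows but does not close, because both can fall in the same short episode.

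Third, the largest assumed excess, 20 per 20,000, equals a full year of expected hemorrhagic strokes, and 6 months is the horizon at which the distortion is greatest. This is correct, so all three horizons are shown.

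Fourth, the plotted curve and the separate description of subtypes would let a reader notice an early excess. They help, but neither yields a risk ratio free of the early events.

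Finally, it can be said that sensitivity analyses belong in an analysis plan. Here the protocol itself fixes the start of follow-up, the code lists and the content of 8.7.2.5, and Appendix A lists no stand-alone documents.

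**Conclusion.** The point holds as a gap in protection. Stroke counting starts at once, the pooled outcome includes conditions that can be mistaken for migraine at index, and no planned analysis sets early events aside. The resulting bias in the erenumab versus anti-epileptic ratio may plausibly be downward. At the assumed excesses a true 1.5 reads between 1.12 and 1.47, depending on count and horizon.

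A reader might infer that such strokes certainly occur, that they fall mostly among anti-epileptic starters, or that they would hide a harm altogether. The documents support none of these. They give no counts, the arm difference is an inference, and no scenario above brings a true 1.5 to the null. A ratio of 2.0, the target for proceeding to the comparison, would be reduced but still detected. No mechanism is shown for erenumab versus the other antibodies, and the case for onabotulinumtoxinA is weaker than for anti-epileptics.

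The conclusion rests on three assumptions: some listed strokes present first as headache, anti-epileptics are started nearer to that presentation, and the excess lies in the range shown.

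**What to change.** In 8.7.2.5, prespecify a lagged sensitivity analysis for stroke, mainly for erenumab versus anti-epileptics:

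- Start stroke follow-up after a stated lag, for example on day 31, and label that choice an assumption. Restrict to patients event-free and uncensored at that point, re-estimate the weights in them, and say whether the horizons count from index or from the lagged start.
- Tabulate day 1-30 strokes by arm and subtype. The table is descriptive: with about 10 strokes per arm expected by chance, an excess of 4 could not be told from noise.
- Report the lagged ratio with its confidence interval beside the day-1 ratio. State in advance that a null or low day-1 ratio for this contrast will be interpreted together with the lagged one. Do not use a rule triggered by the two ratios differing, since they nearly always will.

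Reconcile 8.2.2.1 (with Appendix C) and 8.9.1.2 on whether one emergency room migraine claim is enough for the anti-epileptic and onabotulinumtoxinA cohorts. Also align 8.3.2 with 8.2.5 on whether the index date itself counts.

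The cost is one further run of the same program and a few lines of text. The lagged run gives up about 8% of first-year strokes (30/365) and cannot show a very early true effect, which remains visible in the day-1 analysis.

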### Hemorrhagic Stroke Codes

Code	Code type	Code description	Setting (Any diagnosis position)
160	ICD-10-CM Diagnosis	Nontraumatic subarachnoid hemorrhage	1 IP
160.0	ICD-10-CM Diagnosis	Nontraumatic subarachnoid hemorrhage from carotid siphon and bifurcation	1 IP
160.00	ICD-10-CM Diagnosis	Nontraumatic subarachnoid hemorrhage from unspecified carotid siphon and bifurcation	1 IP
l60.01	ICD-10-CM Diagnosis	Nontraumatic subarachnoid hemorrhage from right carotid siphon and bifurcation	1 IP
160.02	ICD-10-CM Diagnosis	Nontraumatic subarachnoid hemorrhage from left carotid siphon and bifurcation	1 IP
160.1	ICD-10-CM Diagnosis	Nontraumatic subarachnoid hemorrhage from middle cerebral artery	1 IP

Code	Code type	Code description S	
160.10	ICD-10-CM Diagnosis	Nontraumatic subarachnoid hemorrhage from unspecified middle cerebral artery	1 IP
160.11	ICD-10-CM Diagnosis	Nontraumatic subarachnoid hemorrhage from right middle cerebral artery	1 IP
160.12	ICD-10-CM Diagnosis	Nontraumatic subarachnoid hemorrhage from left middle cerebral artery	1 IP
160.2	ICD-10-CM Diagnosis	Nontraumatic subarachnoid hemorrhage from anterior communicating artery	1 IP
160.20	ICD-10-CM Diagnosis	Nontraumatic subarachnoid hemorrhage from unspecified anterior communicating artery	1 IP
160.21	ICD-10-CM Diagnosis	Nontraumatic subarachnoid hemorrhage from right anterior communicating artery	1 IP
160.22	ICD-10-CM Diagnosis	Nontraumatic subarachnoid hemorrhage from left anterior communicating artery	1 IP
160.3	ICD-10-CM Diagnosis	Nontraumatic subarachnoid hemorrhage from posterior communicating artery	1 IP
160.30	ICD-10-CM Diagnosis	Nontraumatic subarachnoid hemorrhage from unspecified posterior communicating artery	1 IP
160.31	ICD-10-CM Diagnosis	Nontraumatic subarachnoid hemorrhage from right posterior communicating artery	1 IP
160.32	ICD-10-CM Diagnosis	Nontraumatic subarachnoid hemorrhage from left posterior communicating artery	1 IP
160.4	ICD-10-CM Diagnosis	Nontraumatic subarachnoid hemorrhage from basilar artery	1 IP
160.5	ICD-10-CM Diagnosis	Nontraumatic subarachnoid hemorrhage from vertebral artery	1 IP
160.50	ICD-10-CM Diagnosis	Nontraumatic subarachnoid hemorrhage from unspecified vertebral artery	1 IP
160.51	ICD-10-CM Diagnosis	Nontraumatic subarachnoid hemorrhage from right vertebral artery	1 IP
160.52	ICD-10-CM Diagnosis	Nontraumatic subarachnoid hemorrhage from left vertebral artery	1 IP
160.6	ICD-10-CM Diagnosis	Nontraumatic subarachnoid hemorrhage from other intracranial arteries	1 IP
160.7	ICD-10-CM Diagnosis	Nontraumatic subarachnoid hemorrhage from unspecified intracranial artery	1 IP
160.8	ICD-10-CM Diagnosis	Other nontraumatic subarachnoid hemorrhage	1 IP

Code	Code type	Code description	Setting (Any diagnosis position)
160.9	ICD-10-CM Diagnosis	Nontraumatic subarachnoid hemorrhage, unspecified	1 IP
l61	ICD-10-CM Diagnosis	Nontraumatic intracerebral hemorrhage	1 IP
l61.0	ICD-10-CM Diagnosis	Nontraumatic intracerebral hemorrhage in hemisphere, subcortical	1 IP
l61.1	ICD-10-CM Diagnosis	Nontraumatic intracerebral hemorrhage in hemisphere, cortical	1 IP
l61.2	ICD-10-CM Diagnosis	Nontraumatic intracerebral hemorrhage in hemisphere, unspecified	1 IP
161.3	ICD-10-CM Diagnosis	Nontraumatic intracerebral hemorrhage in brain stem	1 IP
l61.4	ICD-10-CM Diagnosis	Nontraumatic intracerebral hemorrhage in cerebellum	1 IP
l61.5	ICD-10-CM Diagnosis	Nontraumatic intracerebral hemorrhage, intraventricular	1 IP
161.6	ICD-10-CM Diagnosis	Nontraumatic intracerebral hemorrhage, multiple localized	1 IP
161.8	ICD-10-CM Diagnosis	Other nontraumatic intracerebral hemorrhage	1 IP
l61.9	ICD-10-CM Diagnosis	Nontraumatic intracerebral hemorrhage, unspecified	1 IP

	1	-		
Characteristic	Treatment Model	Censoring Model	Numerical (N) or categorical (C)	Covariate assessment period*
Demographics	Index Date			
Age (years), 18-24, 25-34, 35-44, 45-54, 55-64	Х	X	С	
Gender (male, female)				
Geographical region (eg, Midwest, Northeast, South, West)	Х	х	С	
Select Migraine Diagnoses				Baseline period
Chronic migraine (without aura)	Х	X	С	
Migraine with aura	Х	Х	С	
Acute Migraine Medications				Baseline period
Triptans	Х	Х	С	
Ergotamines	Х	Х	С	
Nonsteroidal anti- inflammatory drugs (NSAIDs)	Х	X	С	
Opioids	Х	Х	С	
Non-opioid, non-NSAID analgesics	Х	Х	С	
Gepants	Х	Х	С	
Other acute migraine-specific treatments	Х	X	С	
Non-CGRP Mediated Migraine	Preventives			Baseline period
Any MPT	Х	Х	С	
Select anti-depressants	Х	Х	С	
Select anti-epileptics	Х	Х	С	
Botulinum toxins	Х	Х	С	
Other migraine preventive agents	Х	X	С	

# Appendix D: *A Priori* List of Covariates to be Included in the Treatment and Censoring Modelsa

Footnotes defined on last page of table

Page 1 of 4

Characteristic	Treatment Model	Censoring Model	Numerical (N) or categorical (C)	Covariate assessment period*
Healthcare Utilization	Baseline period, Follow-up			
Ambulatory visits	Х	Х	N	
Emergency room visits	Х	Х	N	
Inpatient hospital visits	Х	Х	N	
Pneumococcal vaccination		Х	С	
Influenza vaccination		Х	С	
Herpes zoster vaccination		Х	С	
Eye exam		Х	С	
Screening colonoscopy		Х	С	
Screening PSA test		Х	С	
Screening fecal occult blood test		Х	С	
Screening mammogram		Х	С	
Oxygen equipment use		Х	С	
Home hospital bed		Х	С	
Mobility aids		Х	С	
Mechanical ventilation		Х	С	
Ambulance / life support		Х	С	
Rehabilitation services		Х	С	
Overall Medication Utilization	Baseline period, Follow- up			
Generic medications dispensed	X	Х	N	
Unique drug classes dispensed	Х	Х	N	

Footnotes defined on last page of table

Page 2 of 4

Characteristic	Treatment Model	Censoring Model	Numerical (N) or categorical (C)	Covariate assessment period*
Other Medications				Baseline Period
Contraceptives	Х	Х	С	
Anti-hypertensives	Х	Х	С	
Anti-coagulants	Х	Х	С	
Anti-platelets	Х	Х	С	
Lipid-lowering agents	Х	Х	С	
Anti-diabetics	Х	Х	С	
Cardiac glycosides	Х	Х	С	
Calcium gluconate	Х	Х	С	
Fludrocortisone/ Midodrine	Х	Х	С	
Weight loss prescriptions	Х	Х	С	
Fludrocortisone/ Midodrine	Х	Х	С	
Hyperpolarization-activated cyclic nucleotide-gated channel blocker	Х	X	С	
Comorbidities	I	1	1	Baseline Period
Diabetes mellitus	Х	Х	С	
Hypercholesterolemia	Х	Х	С	
Hypertension	Х	Х	С	
Liver disease / Cirrhosis	Х	Х	С	
Depression	Х	Х	С	
Chronic Obstructive Pulmonary Disease (COPD)	Х	X	С	
Renal Disease	Х	Х	С	
Cardiac arrhythmia	Х	Х	С	
Asthma	Х	Х	С	
Human immunodeficiency virus (HIV)	Х	Х	С	
Lupus	Х	Х	С	
Epilepsy/Seizure/Convulsions	Х	Х	С	
Anxiety	Х	Х	С	

Footnotes defined on last page of table

Page 3 of 4

Characteristic	Treatment Model	Censoring Model	Numerical (N) or categorical (C)	Covariate assessment period*
Comorbidities (continued)			Baseline Period	
Depression	Х	Х	С	
Peripheral Artery Disease	Х	Х	С	
Venous thromboembolism	Х	Х	С	
Critical limb ischemia	Х	Х	С	
Myocardial Ischemia	Х	Х	С	
Congestive heart failure	Х	Х	С	
Acute myocardial infarction	Х	Х	С	
Unstable angina	Х	Х	С	
Prinzmetal angina	Х	Х	С	
Other and unspecified angina pectoris	Х	Х	С	
Acute atrial fibrillation	Х	Х	С	
Paroxysmal atrial fibrillation	Х	Х	С	
Acute ventricular fibrillation	Х	Х	С	
Premature atrial contractions	Х	Х	С	
Acute ventricular tachycardia	Х	Х	С	
Coronary revascularization	Х	Х	С	
Ischemic/hemorrhagic stroke	Х	Х	С	
Sub-arachnoid stroke	Х	Х	С	
Unspecified stroke	Х	Х	С	
Transient ischemic attack	Х	Х	С	
Other acute cerebrovascular events	Х	Х	С	
Other ischemic cerebrovascular events	Х	Х	С	

Page 4 of 4

a Additional variables predictive of treatment assignment or censoring may be added to the respective models, based on identification of the most common diagnoses, procedures, and medications identified in the study population.

